
2. INTRODUCTION

This statistical analysis plan describes the statistical analysis plan for the special investigation (Study 7471048) (hereinafter referred to as this study) for VIZIMPRO Tablets (dacomitinib hydrate) (hereinafter referred to as this drug). In this document, texts cited from the protocol are indicated in *italics*.

2.1. Study Design

This drug blocks abnormal signals and inhibit tumor cell proliferation by irreversibly inhibiting the tyrosine kinase activity of epidermal growth factor receptor (EGFR) and mutated EGFR (e.g., deletion of exon 19, point mutation of L858R in exon 21) and other receptors of the ErbB receptor family, HER2 (ErbB2) and HER4 (ErbB4), and by irreversibly inhibiting the activity of homo and heterodimer formed by the ErbB receptor family [EGFR, HER2, ErbB3 (HER3), and HER4]. The marketing authorization of this drug was obtained in January 2019 in Japan as an indication of “EGFR mutation-positive inoperable or recurrent non-small cell lung cancer (NSCLC)”.

This study is a multicenter cohort study of patients treated with this drug. The investigators complete the CRF based on the information required by the study that are extracted from medical records such as medical charts created in daily medical practice. This study will be conducted in patients with EGFR mutation-positive inoperable or recurrent NSCLC who have not received this drug.

The planned period covered by this study is as follows.

Investigation period: July 2019 to March 2026

*Registration period: July 2019 to March 2025**

**: The registration is terminated if the target number of the patients has been collected, even before the end of the registration period.*

The observation period will be 52 weeks from the first day of administration of this drug. However, the observation period will be until the date of treatment discontinuation for patients who discontinue treatment with this drug (adverse events will be reported until 28 days after the date of treatment discontinuation).

799 patients with EGFR mutation-positive inoperable or recurrent NSCLC (safety analysis set)

Rationale for the sample size

In Japanese NSCLC patients treated with single-agent dacomitinib at the starting dose of 45 mg QD, the incidence of all-causality ILD was 5.9% (6/101 patients). In order to evaluate the effect of risk factors for ILD under the actual status of use of this drug, the sample size was set so that a statistically significant relative risk can be detected between subgroups with and without risk factors. Assuming that the incidence of ILD in the low-risk and high-risk populations is 5.9% and 11.8%, respectively (equivalent to 2.0 relative risks), and that the ratio of the number of subjects in the low-risk and high-risk populations is 1: 3, the number of patients in whom risk factors can be detected under a significance level (two-sided) of

15% and a power of 80% is 799. Assuming that 10% of the enrolled patients will be excluded from the safety analysis set for some reason, the number of enrolled patients was set at 888.

2.2. Study Objectives

This study investigates the following in patients with EGFR mutation-positive inoperable or recurrent NSCLC under post-marketing actual status of use of this drug because interstitial lung disease (ILD) was observed in clinical studies of this drug and the incidence was high in Japanese patients, and ILD has also been observed with other EGFR tyrosine kinase inhibitors and it is considered as an adverse event requiring special attention.

The end of the registration period of this study was March 31, 2025. However, 40 patients were registered until that time, and the registration in this study was terminated before the target sample size of 799 patients (888 patients to be registered) was reached. As a result, the initially planned analyses to investigate risk factors are considered to be less significant. Thus, instead of performing these analyses, risk factors will be evaluated to the extent possible based on the information such as patient background of the patients developing interstitial lung disease.

3. INTERIM AND FINAL ANALYSES

In this study, interim analyses for Periodic Safety Update Reports will be performed periodically. At the time of interim analyses, only the analyses necessary for the Periodic Safety Update Reports among the statistical analyses specified in this plan will be performed. In addition, the final analysis for the re-examination application will be performed. At the time of the final analysis, all analyses specified in this plan will be performed.

4. HYPOTHESES AND DECISION RULES

This study is not a confirmatory investigation. Therefore, any test will be considered as exploratory.

4.1. Statistical Hypothesis

Unless otherwise specified, any test will be two-sided and the significance level will be 5%.

4.2. Statistical Decision Rules

Not applicable.

5. ANALYSIS SETS

5.1. Safety Analysis Set

The safety analysis set consists of a full analysis set that is as closer as possible to all patients who received this drug. More specifically, the safety analysis set is defined as the population of patients registered or reported, excluding those meeting at least one of the following conditions:

1. The case report form could not be collected at all (Description in the report: “Case report form not collected”)
2. There was a violation or deficiency in the contract (Description in the report: “Contract violation/deficiency”)
3. Administration of the drug under investigation is not reported at all (Description in the report: “No administration information”)
4. Information on adverse events is not reported at all - No visits after the first prescription day (Description in the report: “No adverse event information - No revisits”)
5. Information on adverse events is not reported at all - The participant revisited after the first prescription day but no description of information (Description in the report: “No adverse event information - No description”)

The “Guidance for Criteria for Inclusion in Analysis Sets and Data Handling in Drug Use Investigations” will be followed for the details of each criterion. For any patient meeting more than one condition, one will be adopted in order of priority of 1, 2, 3, 4, and 5 and included in the tabulation.

5.2. Efficacy Analysis Set

The efficacy analysis set is defined as the population of patients in the safety analysis set, excluding those meeting at least one of the following conditions:

1. Efficacy evaluation is not reported at all (Description in the report: “No efficacy information”)
2. Disease is not under investigation (Description in the report; “Disease not under investigation”)

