### 8.3.10. Effectiveness evaluation

The effectiveness of this drug will be evaluated for the effectiveness evaluation variables in "Response Evaluation Criteria in Solid Tumors Guidelines - Revised Version 1.1 -" for each separate booklet of the CRFs, and the results will be recorded. If administration of this drug is discontinued, the evaluation before discontinuation of this drug should be recorded.

Assessment of tumor response: Tumor response will be assessed according to RECIST criteria. In the classification of tumor lesions at the start of administration of this drug, target lesions and non-target lesions will be identified, and in addition to the results of assessment of tumor response in each tumor lesion during the observation period, presence or absence of new lesions will be confirmed to evaluate overall response.

PFIZER CONFIDENTIAL

1. Presence or absence of target lesions at the start of administration of this drug
2. Evaluation after the start of administration of this drug

Presence or absence of effectiveness evaluation

Date of best overall response assessment

Best overall response (CR, PR, SD, PD, not evaluable)

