#### **8.7. Data analysis**

##### **1. Analysis sets**

The safety analysis set (SAS) consists of a full analysis set (FAS) that is as closer as possible to all patients who received this drug. The effectiveness analysis set consists of the SAS excluding patients such as those with non-target diseases for whom no effectiveness evaluation has been reported at all. Detailed definitions will be provided in the statistical analysis plan (SAP).

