##### **2. Method of analysis**

- **Safety analysis**

The number and proportion of patients with ILD will be tabulated by subgroup by risk factor. ILD based on the evaluation by an external medical specialist (See 8.3.7.) will be analyzed separately. In addition, the number and proportion of patients with adverse reactions will be tabulated. The details of other analysis plans will be described in the SAP.

- **Effectiveness analysis**

The efficacy rate will be calculated. The efficacy rate is defined as the proportion of patients with a best overall response of CR or PR in the effectiveness analysis set. Further details of the analysis plan will be provided in the SAP.

Detailed methodology for summary and statistical analyses of data collected in this study will be documented in a Statistical Analysis Plan (SAP), which will be dated, filed and

maintained by the sponsor. The SAP may modify the plans outlined in the protocol; any major modifications of primary endpoint definitions or their analyses would be reflected in a protocol amendment.

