6.2. Efficacy Endpoint

- Best overall response (according to the "Response Evaluation Criteria in Solid Tumors Guidelines - Revised Version 1.1")

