7. HANDLING OF MISSING DATA

If the seriousness, causal relationship, action taken, and outcome of interstitial lung disease are missing, the data will be handled as “unknown” for tabulation.

Any missing efficacy endpoint will not be imputed.

The strategy for handling data with uncompleted cleaning is as follows.

- Item of missing data: The item will be handled as missing (category of categorical variables is “unknown”) for both tabulation and listing.
- Item of inconsistent data: The item will be handled as missing for both tabulation and listing. However, a listing of data handling will be prepared separately.
- No signature: Any entry in a case report form without the signature of a contracted physician (including a case report form with the signature of an uncontracted physician only) will be handled as missing for both tabulation and listing.

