8.2.4. Efficacy Analysis

8.2.4.1. Best Overall Response

For the efficacy analysis set and the efficacy analysis set consisting of consented patients, the numbers and proportions of patients with each best overall response will be calculated. In addition, the efficacy rate (proportion of patients with a best overall response of CR or PR) and its two-sided 95% confidence interval (exact method) will be calculated. For the calculation of the efficacy rate, patients not reporting a best overall response will be considered to have achieved a best overall response other than CR or PR.

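### Patients with no efficacy evaluation leave the denominator before the non-responder rule applies, so the efficacy rate needs a companion line that counts them

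*SAP*

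**What the plan says.** SAP section 5.2 builds the efficacy set from the safety set with two exclusions. One covers patients whose disease is not the one under investigation. The other applies where "Efficacy evaluation is not reported at all". This follows protocol section 8.7 (Analysis sets), which removes patients "for whom no effectiveness evaluation has been reported at all".

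Protocol section 8.7 (Method of analysis) defines the efficacy rate as the "proportion of patients with a best overall response of CR or PR in the effectiveness analysis set". SAP section 8.2.4.1 calculates it, with an exact two-sided 95% interval, on the efficacy set and on the efficacy set of consented patients. It adds that, for this rate, "patients not reporting a best overall response will be considered to have achieved a best overall response other than CR or PR".

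SAP section 7 says: "Any missing efficacy endpoint will not be imputed". Best overall response is the only efficacy endpoint in SAP section 6.2, so sections 7 and 8.2.4.1 concern the same variable. Neither refers to the other.

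On data capture, protocol section 8.3.10 records "Presence or absence of effectiveness evaluation" as an item separate from the best overall response, which has its own category for not evaluable. For patients who stop the drug, the assessment made before stopping is the one recorded. Protocol section 8.2.6 ends the observation period at discontinuation, apart from 28 further days of adverse event reporting.

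**The concern.** A non-responder rule is normally there so that patients without a response assessment do not flatter the response rate. Here the set definition acts first. Patients with no assessment at all, the group for whom such a rule matters most, have already left the denominator, and the rule covers only those who stay in the set without a usable best overall response.

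Whether a patient has an assessment can depend on how treatment went. Someone who stops before the first tumour assessment may have nothing to record, and the discontinuation reasons in protocol section 8.3.8 include lack of effect, adverse events and death. The exclusion may therefore be related to outcome. With only 40 patients registered (SAP section 2.2), a handful of such exclusions would move the reported percentage visibly, and no planned line shows by how much.

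**Working it through.** **Any figure in the plan to reproduce.** There is none for this point. The plan gives no expected response rate and no expected number of unevaluated patients. Its one design calculation (799 analysed, 888 enrolled) concerns ILD risk factors and does not bear on the efficacy rate.

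**Inputs.**
- N: safety-set patients with the target disease. At most 40, the number registered (SAP section 2.2). I use 40 as the upper bound.
- m: those among them with no efficacy evaluation. Not in the documents; assumed 0, 2, 4 or 8.
- x: patients with CR or PR. Not in the documents; set so that the planned rate is near 60%.

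**Formulas.**
- Rate as planned: x/(N−m).
- Rate with unevaluated patients counted as not CR/PR: x/N.
- Ratio of the two: N/(N−m), which is never below 1.
- Difference: x·m/[N(N−m)], which is never negative and is zero when m = 0.

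**Results for N = 40** (exact 95% intervals in brackets).

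| m | As planned | All counted | Gap |
|---|---|---|---|
| 0 | 24/40 = 60.0% (43.3–75.1) | 24/40 = 60.0% (43.3–75.1) | 0 points |
| 2 | 23/38 = 60.5% (43.4–76.0) | 23/40 = 57.5% (40.9–73.0) | 3.0 points |
| 4 | 22/36 = 61.1% (43.5–76.9) | 22/40 = 55.0% (38.5–70.7) | 6.1 points |
| 8 | 19/32 = 59.4% (40.6–76.3) | 19/40 = 47.5% (31.5–63.9) | 11.9 points |

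Check at m = 4: 22 × 4 / (40 × 36) = 88/1440 = 6.1 points.

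**Sensitivity to the assumptions, at m = 4.**
- Planned rate near 40%: 14/36 = 38.9% against 14/40 = 35.0%, a gap of 3.9 points.
- Planned rate of 75%: 27/36 = 75.0% against 27/40 = 67.5%, a gap of 7.5 points.
- Smaller N, with N = 36: 19/32 = 59.4% against 19/36 = 52.8%, a gap of 6.6 points.

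**Sections 7 and 8.2.4.1 side by side.** Take an efficacy set of 36 with 22 responders and, as an assumption, 2 patients whose best overall response is missing. Under section 8.2.4.1 the two count as not CR/PR: 22/36 = 61.1%. Under section 7 their response stays missing. They are then not in the numerator, but they are still in the set that the protocol names as denominator: again 22/36 = 61.1%. Only an analyst who also removed them from the denominator would get a different figure (22/34 = 64.7%), and that departs from the protocol's definition.

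**The case against.** The exclusion is prespecified, matches the protocol's own effectiveness set, and is disclosed: SAP section 8.2.1.1 tabulates exclusions by reason and section 8.2.1.3 lists the patients. Efficacy is not the study objective, all tests are exploratory (SAP section 4), and no decision rests on this rate. All of this stands. It is why the protocol-defined rate should remain the lead figure. Disclosure is only a partial answer, because section 8.2.1.1 names no disposition counts for the consented sets, on which the rate is also reported.

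Four stronger readings are tempting, and the documents do not support them.

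- *Section 7 forbids the non-responder rule, so the SAP contradicts itself and yields two denominators.* Section 7 is general and section 8.2.4.1 is specific to one calculation. Section 7 can be read as saying that no response category is filled in. With the protocol's denominator both give the same rate. What is missing is a cross-reference.
- *The non-responder rule is empty.* It is not. Evaluation status is recorded separately from best overall response, and section 7 sets inconsistent or unsigned entries to missing. Patients can therefore be in the set without a usable response and be counted as non-responders.
- *The excluded patients are mainly treatment failures.* No section says so. The discontinuation reasons also include not returning and transfer elsewhere, and protocol section 8.9 accepts that chart data may simply be absent. An early stopper with progression or a not-evaluable result on record stays in the denominator.
- *The rate is inflated and its interval misplaced.* That presumes that the target is an all-patients rate with non-evaluation counted as failure, which the plan does not adopt. The true response of unevaluated patients is unknown. At m = 4 with 22 responders it could lie anywhere from 22/40 = 55.0% to 26/40 = 65.0%, and the planned 61.1% falls inside that range.

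**Conclusion.** The point holds in a limited form. The set definition takes patients with no efficacy evaluation out of reach of the non-responder rule, the exclusion can depend on outcome, and the planned rate can only equal or exceed the rate that counts those patients as not CR/PR. The direction and the factor N/(N−m) follow from the definitions alone.

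The size does not. The gaps in the table, from none to about 12 points, rest on an assumed N of 40, an assumed rate near 60% and assumed values of m; if every patient has an evaluation, there is no effect. The wording of section 7 is a clarification and does not change the rate. Overall this is a cheap improvement to the reporting of a non-primary endpoint, not a fault that invalidates the planned rate.

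**What to change.** 1. Keep the protocol-defined efficacy rate as it is. In SAP section 8.2.4.1 add one line giving the efficacy rate and its exact two-sided 95% interval over all safety-set patients with the target disease, with no evaluation or a missing best overall response counted as not CR/PR. Not-evaluable patients are already non-responders within the set and need no new rule.
2. Give the same line for consented patients, using the consented safety set restricted to the target disease.
3. In SAP section 7, qualify the no-imputation sentence with: *except as specified in 8.2.4.1 for the efficacy rate*.

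The added line has a further benefit. It does not depend on where the boundary falls between having no reported evaluation and having no reported best overall response, since both count the same way.

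The cost is one extra row per set in the response table, a short SAP edit, and a figure that may be somewhat less favourable shown beside the current one. No new data are needed. The change is best made before the database release planned for August 2026 (protocol section 5).

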5.3. Other Analysis Sets

5.3.1. Safety Analysis Set Consisting of Consented Patients

The safety analysis set consisting of consented patients is defined as the population of patients registered or reported and providing consent for dissemination and publication of study results, excluding those meeting at least one of the conditions in Section 5.1.

5.3.2. Efficacy Analysis Set Consisting of Consented Patients

The efficacy analysis set consisting of consented patients is defined as the population of patients registered or reported, excluding those meeting at least one of the conditions in Section 5.2 from the safety analysis set consisting of consented patients.

5.4. Subgroups

Subgroup analyses of safety will be performed for the following patient characteristics:

- Age group [<15 years, ≥ 15 to <65 years, ≥ 65 years]

- Complication: Hepatic impairment [absent, present]
- Complication: Renal impairment [absent, present]

Subgroup analyses of safety will be performed for the following other factor:

- Pregnancy status (female only) [absent, present]

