**STUDY INFORMATION**

Title	Special investigation for VIZIMPRO Tablets
Protocol number	A7471048
Protocol version identifier	Amended 5
Date	18 July 2024
Active substance	Dacomitinib hydrate
Medicinal product	VIZIMPRO Tablets 15 mg/VIZIMPRO Tablets 45 mg
Research question and objectives	To investigate risk factors for interstitial lung disease (ILD) in patients with epidermal growth factor (EGFR) receptor mutation-positive inoperable or recurrent non-small cell lung cancer (NSCLC) under post-marketing actual status of use of VIZIMPRO
Country of study	Japan
Author	PPD

090177e1a1853d10\Final\Final On: 30-Aug-2024 07:48 (GMT)

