**8.3.4. Prior radiotherapy for NSCLC**

The following information on the history of radiotherapy performed from baseline to the end of the observation period (or date of discontinuation) should be recorded.

1. Site

2. Treatment period

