6.4. Covariates

The known risk factors for drug-induced lung injury include age of ≥ 60 years, past pulmonary lesion (especially interstitial pneumonia), post-lung surgery patients, decreased respiratory functions, oxygen therapy, irradiation to the lung, and presence of renal disorder.

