- Oxygen administration for treatment of respiratory disease (categorical [absent, present, unknown])
- Number of prior therapies for NSCLC (including EGFR-TKI) (categorical [0, 1, 2, 3, 4, ≥5])
- History of drug therapy for NSCLC (categorical [absent, present])
- History of drug therapy for NSCLC (EGFR-TKI) (categorical [absent, present])
- History of previous drug therapy for NSCLC
 - EGFR-TKI (1) (categorical [absent, present])
 - EGFR-TKI (2) (categorical [absent, afatinib, gefitinib, erlotinib, osimertinib])
 - Chemotherapy (categorical [absent, present])
 - History of other specific drug therapy (by therapeutic class [subclass]) (categorical [absent, present])
- Past illness (categorical [absent, present])
- Past illness: Interstitial lung disease (categorical [absent, present])
- Past illness: Lung lesion (excluding interstitial lung disease) or decreased respiratory function (categorical [absent, present])

The disease name (PT) corresponding to lung lesion (excluding interstitial lung disease) or decreased respiratory function should be asthma/bronchospasm (SMQ narrow), respiratory failure (SMQ narrow), or “chronic obstructive pulmonary disease.”

- Complication: (categorical [absent, present])
- Complication: Interstitial lung disease (categorical [absent, present])
- Complication: Lung lesion (excluding interstitial lung disease) or decreased respiratory function (categorical [absent, present])
- Complication: Hepatic impairment (categorical [absent, present])
- Complication: Renal impairment (categorical [absent, present])

For disease names (PT) corresponding to hepatic/renal impairment, the latest “procedure for extraction of hepatic/renal impairment” will be followed.

- History of surgery for NSCLC (categorical [absent, present])
- Prior radiotherapy for NSCLC (categorical [absent, present])

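### SAP version 2.0 crosses ILD with only one of its seven named risk factors as named, and specifies no output for the case-background evaluation that replaces the risk-factor analysis

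*SAP*

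**What the plan says.** - **Objective.** The Protocol's study information page gives a single aim: "To investigate risk factors for interstitial lung disease (ILD) in patients with epidermal growth factor (EGFR) receptor mutation-positive" NSCLC. Section 7 lists nothing else.
- **Protocol 8.7 (Amended 5, July 2024).** "The number and proportion of patients with ILD will be tabulated by subgroup by risk factor". The same section lets the SAP modify the outlined plans, and says that major changes to primary endpoint definitions or their analyses would go into a protocol amendment.
- **SAP 6.4.** Known risk factors for drug-induced lung injury are age of 60 or over and "past pulmonary lesion (especially interstitial pneumonia), post-lung surgery patients, decreased respiratory functions, oxygen therapy, irradiation to the lung, and presence of renal disorder".
- **SAP 5.4 and 8.2.3.4 (version 2.0, April 2025).** "Subgroup analyses of safety will be performed for the following patient characteristics": "Age group [<15 years, ≥ 15 to <65 years, ≥ 65 years"], hepatic impairment and renal impairment. Pregnancy is added as another factor. The number and proportion with ILD are tabulated for these factors. The amendment table in SAP Section 1 says the list was limited to backgrounds used in the re-examination application.
- **SAP 2.2.** After reporting 40 registered patients, it drops the planned analyses and says "risk factors will be evaluated to the extent possible based on the information such as patient background of the patients developing interstitial lung disease".
- **SAP 8.2.2.1.** Lung history, oxygen use, surgery and radiotherapy are summarised for the safety and efficacy analysis sets, for example "Prior radiotherapy for NSCLC (categorical [absent, present"]). Protocol 8.3.4 collects the site and treatment period for the "history of radiotherapy performed from baseline to the end of the observation period". Protocol 8.3.3 collects site and date for surgery.

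**The concern.** The tables that cross ILD with a patient characteristic were chosen to match a regulatory form, not the ILD question. The factors that the SAP itself regards as relevant to lung injury are mostly not set against ILD anywhere. The amendment table says that disease and treatment history thought to affect ILD onset was added to 8.2.2.1 in version 2.0, yet that section reports it for whole analysis sets, not by ILD status.

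The promised replacement is a look at the backgrounds of the ILD cases, with no stated table, listing or comparison group. A trait shared by the cases may simply be common in the cohort. With a handful of cases, a narrative without a stated comparison is easy to over-read. The sole objective would then rest on an unspecified review, while the Protocol still promises tabulation by risk factor.

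**Working it through.** **1. The two lists side by side**

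| Factor in SAP 6.4 | Crossed with ILD (5.4, 8.2.3.4) | Summarised in 8.2.2.1 |
|---|---|---|
| Age 60 or over | Yes, but split at 65 | Continuous, and bands at 15 and 65 |
| Past pulmonary lesion, especially interstitial pneumonia | No | Yes (past and concurrent, ILD and other lesion) |
| Lung surgery | No | Any NSCLC surgery, no site |
| Decreased respiratory function | No | Yes (combined with other lung lesion) |
| Oxygen therapy | No | Yes |
| Lung irradiation | No | Any NSCLC radiotherapy, no site |
| Renal disorder | Yes | Yes |

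One of seven is crossed as named, one with a different cut (patients aged 60 to 64 fall in the lower stratum), and five not at all. Hepatic impairment and pregnancy are crossed with ILD but are not on the 6.4 list.

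**2. Outputs for the SAP 2.2 evaluation.** Section 8 contains no table of backgrounds by ILD status. Section 8.2.3 mentions event listings. Section 9 names a listing of patients with adverse reactions, a laboratory listing and regulatory forms. Nothing says that any of these shows the 6.4 factors for each ILD case.

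**3. The design figure.** Inputs from Protocol 8.5.2: ILD rates 5.9% (low risk) and 11.8% (high risk), relative risk 2.0, low:high ratio 1:3, two-sided 15%, power 80%. The Wald formula on the log relative risk is

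n_low = (z_0.925 + z_0.80)² × [(1 − p1)/p1 + (1 − p2)/(3 p2)] / (ln 2)²

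= (1.4395 + 0.8416)² × (15.949 + 2.492) / 0.4805 = 199.7

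The total is 4 × 199.73 = 798.9, so 799, and 799/0.9 = 888 to enrol. Both stated figures reproduce.

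**4. The same formula at 40 patients.** With 10 low-risk and 30 high-risk patients, SE = √(15.949/10 + 7.475/30) = 1.358 and ln 2/SE = 0.510.

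- Two-sided 15%: Φ(0.510 − 1.440) = 17.6%.
- Two-sided 5% (the level in SAP 4.1): Φ(0.510 − 1.960) = 7.4%.
- Ratio reversed to 3:1 (assumption): 20.4% and 8.9%.
- 36 analysed after the planned 10% exclusion, ratio 1:3: 17.0% and 7.0%.

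**5. Expected ILD cases in 40.** 40 × 0.059 = 2.4; design mix 10 × 0.059 + 30 × 0.118 = 4.1; 40 × 0.118 = 4.7. The chance of no case at 5.9% is 0.941^40 = 8.8%.

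**6. What a descriptive table would show.** Assume 28 of 40 patients are aged 60 or over, two ILD cases and no association. Both cases are 60 or over with probability (28 × 27)/(40 × 39) = 48%. If 20 or 32 patients were 60 or over, it would be 24% or 64%. A case-only account would report that every case was 60 or over. The table would show 2/28 (7.1%, exact 95% CI 0.9% to 23.5%) against 0/12 (0% to 26.5%). It does not make that pattern rarer, but it shows how little the pattern means.

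**The case against.** The strongest reply is that nothing here could have rescued the objective. SAP 2.2 and the amendment table disclose the shortfall and the change, and SAP Section 4 calls every test exploratory. Restoring every subgroup would leave power of about 7% to 20%. This stands, and it limits the point to descriptive reporting.

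Second, a reader might infer that the case review has no denominator. The documents do not support that. For factors as categorised in 8.2.2.1, whole-set totals plus the case backgrounds give the with and without counts by subtraction. What is missing is a specified cross-tabulation. For age at 60 and for lung-specific surgery and irradiation, the current categories do not supply the totals.

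Third, SAP 6.4 describes known factors in general and does not prescribe analysis cuts, and age is also summarised as continuous. So the split at 65 is a mismatch with the named factor, not an error in itself.

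Fourth, Table 1 of the Protocol says that surgery and radiotherapy entries include information from before the start of administration, and the SAP labels them as history or prior treatment. A pre-treatment meaning may well be intended. No rule restricts them by site or by date before first dose, so this stands as a secondary point of definition.

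Finally, SAP 8.2.3.5 allows additional analyses. A general permission does not specify an output for the study's only objective.

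**Conclusion.** The point holds as a gap in specification that should be fixed before the final analysis. Five of the seven factors in SAP 6.4 have no ILD-by-factor table, a sixth uses a different cut, and the evaluation promised in SAP 2.2 has no specified output and no stated comparison with non-cases. Protocol 8.7 still commits to tabulation by risk factor. It predates SAP version 2.0, and the documents show no later amendment.

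A reader might go further and conclude that the subgroup list is why the study cannot answer its question, or that the named factors are no longer examined at all. Neither follows. Registering 40 of 888 patients is the main cause. Renal impairment and a form of age are kept, and the other factors are still collected and summarised, though surgery and radiotherapy without restriction to the lung.

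The power and case counts assume the protocol's ILD rates and 1:3 ratio, with all 40 registered patients analysed. The age illustration rests on an assumed age distribution and two assumed cases.

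**What to change.** 1. In SAP 5.4 and 8.2.3.4, add one table of ILD n/N, percentage and exact 95% CI, with and without each factor: age under 60 or 60 and over; past or concurrent ILD; other lung lesion or decreased respiratory function; lung surgery; oxygen administration; lung irradiation; renal impairment. Label it descriptive.
2. In SAP Section 9, add a listing of each ILD case, whatever its causality, against the same factors.
3. Derive lung surgery and lung irradiation from the recorded site, with a date before the first dose.
4. Reword SAP 2.2 so that ILD cases are compared with non-cases. Keep the existing re-examination subgroups.
5. Reconcile Protocol 8.7 with the SAP, and record whether the change counts as one that its amendment rule covers.

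The cost is SAP wording, one table, one listing and a few derivations not now in 8.2.2.1: age at 60, combined ILD history, and site- and date-restricted surgery and radiotherapy. No new data are needed, and the Protocol plans database release for August 2026. The downside is very small cells, which the intervals will show.
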